### Figure 6.1-6-2 CORI Reusable Instruments

CORI Robotic Drill

Checkpoint Pins   Bone Screw

- CORI Robotic Drill:** Controls the position and speed of the bur. It is intended for 75 uses and is able to be autoclaved, auto washed, and disinfected.
- Point Probe:** Tracked instrument used in robotic drill calibration, and bone registration, checkpoint verification.
- Femur & Tibia Trackers:** Rigid arrays placed on the femur and tibia to track the relative position of bones to point probe and robotic drill tools using reflective markers.
- Checkpoint Pins:** placed in femur and tibia and checked periodically with the point probe to verify that the tibia and femur tracking arrays have not moved during the procedure.

Details on single use instruments of CORI can be found in Section 22.3.

CORI, as well as the single use components, are manufactured by Smith+Nephew, Blue Belt Technologies, [name]

#### 6.1.2 Comparator Treatment

CORI will be compared to conventional manual instrumentation currently available in Australia, China (Hong Kong), New Zealand, South Korea, and China Mainland.

#### CONFIDENTIAL AND PROPRIETARY

This document contains information that is confidential and proprietary to Smith & Nephew PLC and Smith & Nephew, Inc. and is intended for use only by Smith+Nephew and its manufacturer. It shall not be reproduced or copied in whole or in part, nor shall the contents be disclosed by any means without prior written permission from Smith+Nephew, nor shall anyone make any use of it that is contrary to the expressed or implied wishes of Smith+Nephew.

Clinical Protocol	Study Number: CORI.2019.06
A Prospective, Multi-center, Randomized Controlled Study to Evaluate the Safety and Effectiveness of REAL INTELLIGENCE™ CORI™ in unicondylar knee arthroplasty (UKA) Procedure	Version: 4.0-Master, 07 Sep 2022
	Page: 41 of 167

Arthroplasty has traditionally used conventional manual instruments to guide placement of the implant and determine bone resection in reference to anatomical landmarks. Manual instruments include intramedullary or extramedullary rods that centralize and align the components according to the surgical plan as shown in Figure 6.1-6-3 & Figure 6.1-6-4.

**Figure 6.1-6-3 Extramedullary rod    Figure 6.1-6-4 Intramedullary rod**

### 6.1.3 Ancillary Product(s)

Not applicable.

## 6.2 PRODUCT USE

CORI has a user's manual (Document ID: 500230, REAL INTELLIGENCE™ CORI™ for Knee Arthroplasty). The purpose of this user's manual is to serve as the master reference document for properly trained users in the function and operation of CORI and its accessories.

In addition, the following devices are packaged with an IFU to ensure that the device is used properly and for the intended purposes:

#### CONFIDENTIAL AND PROPRIETARY

This document contains information that is confidential and proprietary to Smith & Nephew PLC and Smith & Nephew, Inc. and is intended for use only by Smith+Nephew and its manufacturer. It shall not be reproduced or copied in whole or in part, nor shall the contents be disclosed by any means without prior written permission from Smith+Nephew, nor shall anyone make any use of it that is contrary to the expressed or implied wishes of Smith+Nephew.

Clinical Protocol	Study Number: CORI.2019.06
A Prospective, Multi-center, Randomized Controlled Study to Evaluate the Safety and Effectiveness of REAL INTELLIGENCE™ CORI™ in unicondylar knee arthroplasty (UKA) Procedure	Version: 4.0-Master, 07 Sep 2022
	Page: 42 of 167

- IFU REAL INTELLIGENCE™ CORI™ Burs (Document ID: 500172)
- IFU REAL INTELLIGENCE™ CORI™ Flat Markers (Document ID: 500198)
- IFU REAL INTELLIGENCE™ CORI™ Irrigation (Document ID: 500173)
- IFU REAL INTELLIGENCE™ CORI™ Instrumentation Tray (Document ID: 500229)

For Australia, Hong Kong, South Korea, and New Zealand the list of reference documents can be found in Appendix Section 22.3 Instruction For Use & User Manual.

For China mainland, details of the use of CORI can be found in the Investigator's Brochure.

### **6.3 PACKAGING AND LABELLING**

Packaging and labeling are prepared to meet regulatory requirements. Package integrity and labelling should be verified prior to use of the product and confirmed in the eCRF.

#### **6.3.1 Labelling of Investigational Product**

All product components of the CORI System are commercial products in the Australia, China(Hong Kong), South Korea, and New Zealand and are being used as approved. Labeling is done as per the standard commercial packaging.

In China mailand, CORI is a an investigational product. The standard commercial packaging as marketed in the US is used. However, additional labels will be included on the commercial packaging to meet the regulatory requirements for investigational devices in countries where the devices are not approved for marketing.

#### CONFIDENTIAL AND PROPRIETARY

This document contains information that is confidential and proprietary to Smith & Nephew PLC and Smith & Nephew, Inc. and is intended for use only by Smith+Nephew and its manufacturer. It shall not be reproduced or copied in whole or in part, nor shall the contents be disclosed by any means without prior written permission from Smith+Nephew, nor shall anyone make any use of it that is contrary to the expressed or implied wishes of Smith+Nephew.  
TMP-CD-05-01 Clinical Protocol - Device - Revision D; SOP-CD-05 Clinical Protocol

Clinical Protocol	Study Number: CORI.2019.06
A Prospective, Multi-center, Randomized Controlled Study to Evaluate the Safety and Effectiveness of REAL INTELLIGENCE™ CORI™ in unicondylar knee arthroplasty (UKA) Procedure	Version: 4.0-Master, 07 Sep 2022
	Page: 43 of 167

Compatible S+N Knee Implant Systems are commercial products in Australia, China (Hong Kong), New Zealand, and China mainland and are being used as approved.

### **6.3.2 Comparator Product**

Conventional approach with conventional manual instrumentation will be used as the comparison group and there will be no packaging involved with the conventional approach.

S+N Knee Implant Systems are commercial products in Australia, Hong Kong, New Zealand, South Korea, and China mainland and are being used as approved.

## **6.4 PRODUCT ACCOUNTABILITY PROCEDURES**

This study is a post-market study in Australia, Hong Kong, South Korea, and New Zealand. However, the sponsor provides the study sites with CORI System (Console, Optical Tracking Camera, Foot Pedal, Tablet, Display Monitor, Cart, CORI Instrument Trays UKA) as well as with reusable instrumentation (CORI robotic Drill, Point Probe, Femur & Tibia Trackers, Checkpoint Pins). Therefore, the following product accountability procedures will be applied for CORI at all study sites.

The investigational site will maintain an inventory of the investigational product. The Sponsor or its designee will provide a log(s) to facilitate IP inventory control. The log will contain details of receipt, use, returns etc. of IP. All IP accountability logs must be retained in the Investigator Site File (ISF). These records must be available for inspection by the Sponsor, its designees, or by regulatory agencies at any time.

The Study Monitor will ensure that the procedures and records are in place for the appropriate reconciliation of all IP. As part of monitoring, the Study Monitor will check that site personnel are following the proper procedures for accountability and completing all necessary documentation.

#### CONFIDENTIAL AND PROPRIETARY

This document contains information that is confidential and proprietary to Smith & Nephew PLC and Smith & Nephew, Inc. and is intended for use only by Smith+Nephew and its manufacturer. It shall not be reproduced or copied in whole or in part, nor shall the contents be disclosed by any means without prior written permission from Smith+Nephew, nor shall anyone make any use of it that is contrary to the expressed or implied wishes of Smith+Nephew.

TMP-CD-05-01 Clinical Protocol - Device - Revision D; SOP-CD-05 Clinical Protocol

Clinical Protocol	Study Number: CORI.2019.06
A Prospective, Multi-center, Randomized Controlled Study to Evaluate the Safety and Effectiveness of REAL INTELLIGENCE™ CORI™ in unicondylar knee arthroplasty (UKA) Procedure	Version: 4.0-Master, 07 Sep 2022
	Page: 44 of 167

No product accountability procedures will be applied for the S+N Knee Implant Systems as these are commercially available products.

For details on CORI and reusable instrumentation please refer to Section 6.1.1 Investigational Product.

## 6.5 SURGICAL TECHNIQUE

All study related procedures with CORI must be performed according to the user's manual (Document ID: 500230 CORI Robotics for Knee Arthroplasty for Australia, Hong Kong, South Korea, and New Zealand, as well as Investigator's Brochure for China) and according to the according to the surgical technique and IFU of the specific S+N Implant System.

Surgeons selected to participate in this study will be familiar with CORI and have written evidence of training and expertise in the study procedure. The Surgeon will conduct Pre-study in order to establish the expertise of the individual surgeons. The exact number of pre-study cases may be adjusted depending on the level of the individual experience of the surgeon.

CORI Case Reports Forms of the non-randomized cases will be collected as proof of surgeons' experience and for inclusion in the safety analysis set (applicable only at sites in China).

## 6.6 MEDICAL PROCEDURE

There are 3 basic steps in unicondylar knee arthroplasty. The first step is preparing the bone and removing the cartridge from the damaged knee compartment. This will be completed using either the CORI robotic drill or an oscillating saw. The surgeon will then position the metal implants on the damaged side of the femur and tibia using several orthopaedic tools. Finally, a spacer will be inserted between the metal implants to reduce friction when the knee flexes and extends. At various times during

### CONFIDENTIAL AND PROPRIETARY

This document contains information that is confidential and proprietary to Smith & Nephew PLC and Smith & Nephew, Inc. and is intended for use only by Smith+Nephew and its manufacturer. It shall not be reproduced or copied in whole or in part, nor shall the contents be disclosed by any means without prior written permission from Smith+Nephew, nor shall anyone make any use of it that is contrary to the expressed or implied wishes of Smith+Nephew.

TMP-CD-05-01 Clinical Protocol - Device - Revision D; SOP-CD-05 Clinical Protocol

Clinical Protocol	Study Number: CORI.2019.06
A Prospective, Multi-center, Randomized Controlled Study to Evaluate the Safety and Effectiveness of REAL INTELLIGENCE™ CORI™ in unicondylar knee arthroplasty (UKA) Procedure	Version: 4.0-Master, 07 Sep 2022
	Page: 45 of 167

the procedure, the hip-knee-ankle angle (HKA) will be checked using the CORI advanced tracking system or via the use of intramedullary and / or extramedullary rods. How the angle is measured will depend on which treatment arm the subject is randomized to receive. All unicondylar knee arthroplasty is completed using general anaesthetic by a surgical team trained in both the CORI system and the use of standard manual instrumentation.

## 7 SUBJECT ENROLLMENT AND WITHDRAWAL

### 7.1 SUBJECT POPULATION

At least 145 subjects will be enrolled into the study. At least 5 of these subjects will be treated with CORI directly to fulfil the learning needs of the surgeons prior to enrolling, a further 140 subjects who will be enrolled in the randomized stage of the study in up to 8 sites in Australia, Hong Kong, New Zealand, South Korea, and China mainland. Seventy (70) subjects will be enrolled for UKA with the use of the CORI and 70 subjects will be enrolled for UKA with the use of conventional manual instrumentation. Vulnerable subjects will not be enrolled in this study.

## 7.2 INCLUSION CRITERIA

Subjects will be considered qualified for enrollment if they meet the following criteria:

- 1 Subject is a suitable candidate for a UKA procedure using CORI and a compatible S+N Knee Implant System.
- 2 Subject requires a cemented UKA as a primary indication that meets any of the following conditions:
  - a) Non-inflammatory degenerative joint disease, including osteoarthritis
  - b) Avascular necrosis
  - c) Requires correction of functional deformity
  - d) Requires treatment of fractures that were unmanageable using other techniques
- 3 Subject is of legal age to consent and considered skeletally mature ( $\geq 18$  years of age at the time of surgery)
- 4 Subject agrees to consent to and to follow the study visit schedule (as defined in the study protocol and informed consent form), by signing the Ethics Committee (EC) or Institutional Review Board (IRB) approved informed consent form.
- 5 Subject plans to be available through one (1) year postoperative follow-up.
- 6 Applicable routine radiographic assessment is possible.

## 7.3 EXCLUSION CRITERIA

Any one (1) of the following criteria will disqualify a potential subject from participation in the study:

### CONFIDENTIAL AND PROPRIETARY

This document contains information that is confidential and proprietary to Smith & Nephew PLC and Smith & Nephew, Inc. and is intended for use only by Smith+Nephew and its manufacturer. It shall not be reproduced or copied in whole or in part, nor shall the contents be disclosed by any means without prior written permission from Smith+Nephew, nor shall anyone make any use of it that is contrary to the expressed or implied wishes of Smith+Nephew.

Clinical Protocol	Study Number: CORI.2019.06
A Prospective, Multi-center, Randomized Controlled Study to Evaluate the Safety and Effectiveness of REAL INTELLIGENCE™ CORI™ in unicondylar knee arthroplasty (UKA) Procedure	Version: 4.0-Master, 07 Sep 2022
	Page: 47 of 167

- 1 Subject receives a UKA on the index joint as a revision for a previously failed surgery, or need for complex implants, or any other implant than a standard UKA (e.g. stems, augments, or custom made devices).
- 2 Subject has been diagnosed with post-traumatic arthritis
- 3 Subject receives simultaneous bilateral UKA OR a unilateral UKA with contralateral TKA.
- 4 Subject has one or more of the following arthroplasties that are not fully healed and well-functioning, as determined by the investigator:
  - Contralateral primary TKA or UKA, however, the subject can only have one knee enrolled in the study.
- 5 Subject does not understand the language used in the Informed Consent Form.
- 6 Subject does not meet the indication or is contraindicated for UKA according to specific S+N knee system's Instructions for Use (IFU).
- 7 Subject has active infection or sepsis (treated or untreated).
- 8 Subject is morbidly obese with a body mass index (BMI) greater than 40.
- 9 Subject is pregnant or breast feeding at the time of surgery.
- 10 Subject, in the opinion of the Investigator, has advanced osteoarthritis or joint disease at the time of surgery and was better suited for an alternate procedure.
- 11 Subject currently enrolled in another orthopedic clinical trial study.

## CONFIDENTIAL AND PROPRIETARY

This document contains information that is confidential and proprietary to Smith & Nephew PLC and Smith & Nephew, Inc. and is intended for use only by Smith+Nephew and its manufacturer. It shall not be reproduced or copied in whole or in part, nor shall the contents be disclosed by any means without prior written permission from Smith+Nephew, nor shall anyone make any use of it that is contrary to the expressed or implied wishes of Smith+Nephew.

Clinical Protocol	Study Number: CORI.2019.06
A Prospective, Multi-center, Randomized Controlled Study to Evaluate the Safety and Effectiveness of REAL INTELLIGENCE™ CORI™ in unicondylar knee arthroplasty (UKA) Procedure	Version: 4.0-Master, 07 Sep 2022
	Page: 48 of 167

- 12 Subject has a condition(s) that may interfere with the UKA survival or outcome (i.e., Paget's or Charcot's disease, vascular insufficiency, muscular atrophy, uncontrolled diabetes, moderate to severe renal insufficiency or neuromuscular disease, or an active, local infection).
- 13 Subject in the opinion of the Investigator, has an emotional or neurological condition that would pre-empt their ability or willingness to participate in the study including mental illness, intellectual disability, drug or alcohol abuse.
- 14 Subject, in the opinion of the Investigator, has a neuromuscular disorder that prohibited control of the index joint.
- 15 Subject is a prisoner or meets the definition of a Vulnerable Subject per ISO 14155:2020 Section 3.55.

 ISO 14155:2020 Section 3.55 States: Vulnerable subject – Individuals who are unable to fully understand all aspects of the investigation that are relevant to the decision to participate, or who could be manipulated or unduly influenced as a result of a compromised position, expectation of benefits or fear of retaliatory response

## 7.4 SCREENING

Investigators should consecutively screen all subjects presenting with degenerative joint disease of the knee, requiring correction of functional deformity, or treatment of fractures that were unmanageable using other techniques to determine whether they meet all inclusion and none of the exclusion criteria.

Participating study sites are required to document all screened subjects considered for inclusion in this study. If a subject is excluded from the study, the reasons for exclusion will be documented in the subject's source documents and noted on the Screening and Enrollment Log. All screening activities that occur prior to consent shall be referred to as pre-screening.

In China sites, part of the screening process will include documentation of women's childbearing potential. If the woman is not of childbearing potential this should be documented in the medical history (e.g., surgically postmenopausal, postmenopausal [i.e., at least one year without menses]). For women of childbearing potential, their method of birth control should be documented in the source.

## 7.5 INFORMED CONSENT

Before conducting any study procedures or examinations, the purpose and nature of the study should be explained to the subject in their native language.

The subject, or their legally authorized representative (if applicable), will then **read, sign, and personally date** the IRB/IEC-approved informed consent document(s) (see below for difficulties with reading and writing). Additionally, the individual who obtains consent from the subject will sign and date the informed consent document.

### CONFIDENTIAL AND PROPRIETARY

This document contains information that is confidential and proprietary to Smith & Nephew PLC and Smith & Nephew, Inc. and is intended for use only by Smith+Nephew and its manufacturer. It shall not be reproduced or copied in whole or in part, nor shall the contents be disclosed by any means without prior written permission from Smith+Nephew, nor shall anyone make any use of it that is contrary to the expressed or implied wishes of Smith+Nephew.

TMP-CD-05-01 Clinical Protocol - Device - Revision D; SOP-CD-05 Clinical Protocol

Clinical Protocol	Study Number: CORI.2019.06
A Prospective, Multi-center, Randomized Controlled Study to Evaluate the Safety and Effectiveness of REAL INTELLIGENCE™ CORI™ in unicondylar knee arthroplasty (UKA) Procedure	Version: 4.0-Master, 07 Sep 2022
	Page: 50 of 167

A copy of the signed informed consent document will be provided to the subject, a copy will be placed in the subject's medical record, with the original filed in the ISF.

If the subject is unable to read, the informed consent document and associated study information may be read aloud to the subject in the presence of an impartial witness. If possible, the subject shall sign and personally date the Informed Consent Form (ICF). Where this is not possible, due to difficulties in writing, the subject shall provide verbal consent to participate in the study. The witness shall then personally sign and date the informed consent form, attesting that the information was accurately explained and that the informed consent was freely given.

ICFs will comply with applicable laws and regulations in Australia (Privacy Act 1988), China, South Korea, and New Zealand (Privacy Act 1993). If new information becomes available during the course of the study that can significantly affect a subject's future health and medical care, Smith + Nephew will ensure that information shall be provided to the subject(s) affected in written form and if relevant, all affected subjects shall be asked to confirm their continuing consent in writing.

## 7.6 ENROLMENT

Subjects for whom the consent process has been completed and have been treated with the study product are considered enrolled.

Subjects that provided informed consent but do not receive the study treatment for any reason will be considered as screen failure.

## 7.7 LOST TO FOLLOW-UP

A subject will be considered lost to follow-up if he/she does not appear for the scheduled study visit for two (2) consecutive visits, and study personnel is unable to contact the subject.

### CONFIDENTIAL AND PROPRIETARY

This document contains information that is confidential and proprietary to Smith & Nephew PLC and Smith & Nephew, Inc. and is intended for use only by Smith+Nephew and its manufacturer. It shall not be reproduced or copied in whole or in part, nor shall the contents be disclosed by any means without prior written permission from Smith+Nephew, nor shall anyone make any use of it that is contrary to the expressed or implied wishes of Smith+Nephew.

TMP-CD-05-01 Clinical Protocol - Device - Revision D; SOP-CD-05 Clinical Protocol

Clinical Protocol	Study Number: CORI.2019.06
A Prospective, Multi-center, Randomized Controlled Study to Evaluate the Safety and Effectiveness of REAL INTELLIGENCE™ CORI™ in unicondylar knee arthroplasty (UKA) Procedure	Version: 4.0-Master, 07 Sep 2022
	Page: 51 of 167

Some actively enrolled subjects will not return for follow-up exams on time. Study personnel must make a reasonable effort to contact the subject and document the following contact attempts before declaring a subject to be lost to follow-up: the subject has been contacted according to the site's policies, but no fewer than two documented phone contacts and one certified letter without response. Copies of all attempts to reach the subjects by mail or email and/or the attempts to contact the subject via other means should be documented, and that documentation should be kept with the subject's source documents.

## 7.8 WITHDRAWAL

### 7.8.1 Withdrawal from Treatment

Subjects may be withdrawn early from having the study treatment at a date close to surgery or during surgery for the following reasons:

- At the discretion of the Investigator due to:
  - A change in treatment is clinically warranted
  - An adverse event
  - Any other significant reason identified by the Investigator

### 7.8.2 Withdrawal from Study

The Investigator may withdraw subjects from the study for many reasons, including but not limited to the following:

- Subject noncompliance (e.g., did not follow instructions, took disallowed medications)
- Subject is lost to follow-up
- The Investigator or the Sponsor terminates the study for any reason
- Concurrent illness
- Adverse Events/Adverse Device Effects

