#### CONFIDENTIAL AND PROPRIETARY

This document contains information that is confidential and proprietary to Smith & Nephew PLC and Smith & Nephew, Inc. and is intended for use only by Smith+Nephew and its manufacturer. It shall not be reproduced or copied in whole or in part, nor shall the contents be disclosed by any means without prior written permission from Smith+Nephew, nor shall anyone make any use of it that is contrary to the expressed or implied wishes of Smith+Nephew.

TMP-CD-05-01 Clinical Protocol - Device - Revision D; SOP-CD-05 Clinical Protocol

Clinical Protocol	Study Number: CORI.2019.06
A Prospective, Multi-center, Randomized Controlled Study to Evaluate the Safety and Effectiveness of REAL INTELLIGENCE™ CORI™ in unicondylar knee arthroplasty (UKA) Procedure	Version: 4.0-Master, 07 Sep 2022
	Page: 52 of 167

- Any other significant reason identified by the Investigator

For each case, the information will be recorded in the subject's source document and the electronic Case Report Form (eCRF), detailing circumstances leading to the withdrawal.

Subjects who withdraw or are withdrawn by the investigator cannot be re-enrolled in the study. Withdrawn subjects will not be replaced.

If at any point during the study, the unicondylar prosthesis needs to be revised for any reason the following will apply: Subjects shall continue to have follow-up visits in order to monitor the subject's health status. Potential data following the revision surgery will not be included as study data but presented separately as safety data.

For minor revisions, where not the whole knee implant system is replaced (e.g. replacement of inserts) the subject shall continue with the study specific schedule and data will be presented.

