#### **Concomitant Medications**

##### Excluded Concomitant Medications

There are no restrictions on concomitant medications for this study.

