### **9.1.9 Discontinued Subjects**

Discontinued subjects are those who voluntarily discontinue participation, who are withdrawn for reasons of safety or use of prohibited concomitant medications/therapies, who are lost to follow-up, refer to Section 7.8 for further details. Where possible, the next scheduled study visit should be completed for all subjects who discontinue the study early. Where consent is withdrawn, the date and any reason given for discontinuation should be captured, at a minimum (see Section 7.8.3).

Finally, if appropriate, the Investigator will also advise the subject of subsequent therapy and/or procedures necessary for their medical condition.

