### 12.5.1 Ongoing Adverse Events at Study Discontinuation

Adverse events which are **related** to a study procedure or S+N IP and are ongoing at the end of subject's participation: The event should be followed until it is either resolved or until the event has become chronic and is not expected to further improve based on Investigator's review of the event.

Adverse events that are **not related** to a study procedure or S+N IP and are ongoing at the end of subject's participation should be followed for 30 days after discontinuation or if the AE is resolved, whichever is sooner.

At the time of data analysis (e.g., interim or final), an evaluation of ongoing events should take place and be listed as ongoing in the safety table.

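### Section 7.8.2 lets the investigator end study participation after surgery because of an adverse event, and no rule then requires the visits beyond the next one, so later events and revisions can be missed in subjects withdrawn because of harm

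*Protocol*

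**What the plan says.** The Protocol separates two kinds of withdrawal. Section 7.8.1 concerns treatment: "Subjects may be withdrawn early from having the study treatment at a date close to surgery or during surgery for the following reasons". Section 7.8.2 concerns the study itself: "The Investigator may withdraw subjects from the study for many reasons, including but not limited to the following". Its list includes "Adverse Events/Adverse Device Effects", concurrent illness, noncompliance (with the taking of a medication that is not allowed as an example) and a final catch-all left to the investigator. The same section adds that "Subjects who withdraw or are withdrawn by the investigator cannot be re-enrolled in the study", and that withdrawn subjects are not replaced.

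Several other provisions bear on what happens next:

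- **7.8.2, revision.** If the prosthesis is revised during the study, "Subjects shall continue to have follow-up visits in order to monitor" the subject's health status. Data after the revision are presented separately as safety data.
- **7.8.4.** Further data collection is barred only when the subject withdraws consent.
- **9.1.9.** Discontinued subjects include those "who are withdrawn for reasons of safety or use of prohibited concomitant medications/therapies". The next scheduled visit is requested, where possible, for everyone who discontinues early.
- **9.1.8.** "There are no restrictions on concomitant medications for this study", and the same is said of concomitant therapies.
- **12.5 and 12.5.1.** A follow-up visit is recommended for an unresolved event at early discontinuation. A related event is followed until it resolves or becomes chronic. An unrelated one "should be followed for 30 days after discontinuation or if the AE is resolved, whichever is sooner".
- **8.4.4 and 10.5.** Adverse events are to be collected from enrolment to study termination or completion. Implant revision rate is a safety endpoint, reported as a proportion with an exact binomial interval in the safety population.

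**The concern.** The treatment is one operation. Once it is done, withdrawal from the study for an adverse event cannot reduce exposure to anything; it only stops scheduled observation. The secondary objective is safety and performance to 12 months, and the subjects most likely to be withdrawn on this ground are those who have already been harmed. Follow-up would then be lost in a way that depends on the outcome being measured.

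What could be missed is new adverse events, re-interventions, later revisions and the 12-month radiographs. The study is not blinded (8.2.2), so the discretion could be used differently in the two arms, although nothing in the documents shows that it would be. Section 10.5 does not say how a subject with incomplete follow-up enters the revision proportion. If such a subject stays in the denominator and a later revision is never seen, the subject counts as unrevised.

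**Working it through.** The plan gives no figure on this point, so there is none to reproduce. The check is whether the other sections close the gap that 7.8.2 opens, followed by an illustration of scale.

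**1. Does 7.8.2 reach the period after surgery?** Yes. Withdrawal close to or during surgery has its own rule in 7.8.1. Section 7.8.2 carries no time limit, and the schedule of events provides for an exit form at the point of withdrawal at the 6-week and 6-month visits.

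**2. What is still collected after such a withdrawal?** The nominal visit days in the schedule are 42, 185 and 365. Section 9.1.9 requests only the next visit.

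| Withdrawn | Next visit, requested where possible | Visits no rule requires | Nominal time left unobserved |
|---|---|---|---|
| After surgery, before the 6-week visit | 6 weeks | 6 and 12 months | 365 − 42 = 323 days |
| Between the 6-week and 6-month visits | 6 months | 12 months | 365 − 185 = 180 days |
| After the 6-month visit | 12 months | none | 0 days |

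If the next visit does not take place, the unobserved time runs from the withdrawal itself. The gap therefore lies mainly with subjects withdrawn before the 6-month visit.

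**3. Do 12.5 and 12.5.1 fill it?** They follow the event that is already ongoing, and for at most 30 days if it is judged unrelated. They do not ask about new events, re-interventions or revisions, and they do not provide the 12-month radiographs.

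**4. Does the revision rule fill it?** It applies to a revision that occurs during the study. On its wording, it does not bring back a subject who was withdrawn for an adverse event and revised later.

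**5. The medication ground.** Sections 7.8.2 and 9.1.9 refer to medications or therapies that are not permitted. Section 9.1.8 restricts none. As written, the ground has nothing to act on and the passages conflict.

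**6. Scale, for illustration only.** Inputs are 70 subjects per arm (Section 11) and 5 revisions in 414 procedures (Section 4.2.4, predecessor NAVIO system).

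- Expected revisions per 70: 70 × 5/414 = 0.85.
- One revision observed: 1/70 = 1.43%. The exact lower limit is 1 − 0.975^(1/70) = 0.04%. The upper limit is the p that solves (1 − p)^70 + 70p(1 − p)^69 = 0.025, which is 7.70%.
- The same revision missed: 0/70 = 0%. The lower limit is 0 and the upper limit is 1 − 0.025^(1/70) = 5.13%.

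With fewer than one revision expected, a single unseen event moves the estimate to zero and the upper limit from 7.7% to 5.1%.

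**The case against.** A reader might infer that safety follow-up simply ends for subjects who were harmed. The documents do not support that. Ongoing events are followed under 12.5 and 12.5.1, one further scheduled visit is requested, and the bar on further data in 7.8.4 covers withdrawal of consent only. The follow-up visits include recording of adverse device effects and a question about revision since the last visit, so that one visit matters; after month 6 it is the 12-month exit visit and nothing scheduled is lost.

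A reader might also see a contradiction between withdrawal for an adverse event and the rule that revised subjects keep attending. There is none. The first is a general permission and the second a specific requirement, and they can stand together. The revision rule does show a principle that the plan does not extend to other harmed subjects.

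Nor is the primary endpoint clearly at risk. For withdrawal before week 6, the visit requested is the one at which the long-leg film is taken. If the film is still missing, counting the subject as a failure is the pre-specified rule in 10.4.1, not a defect of 7.8.2.

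The size is also open to challenge. The documents give no rate of withdrawal for adverse events. The 10% attrition in Section 11 is not broken down by cause and says nothing about harm-related loss. The 5/414 figure does not describe the conventional arm, and the two intervals above overlap almost entirely. All of this stands, and it limits the point to a possible bias of unknown size. The gap before the 6-month visit remains.

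**Conclusion.** The point holds in limited form. Section 7.8.2 allows post-operative withdrawal from the study because of harm, and after one further visit, requested only where possible, nothing requires observation to 12 months. The likely direction of bias in the adverse event and revision summaries is downwards. Its size cannot be derived from the documents; the change from 1/70 to 0/70 assumes one subject who is withdrawn for an adverse event, revised later, not seen again, and kept in a denominator of 70. Different bias by arm is possible in an unblinded study but not shown. The medication wording is a plain inconsistency, but since it has nothing to act on it adds no loss of follow-up.

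For this trial the practical effect is small. SAP Section 2 reports early termination with four subjects enrolled, and Sections 7.1 and 7.15 replace analysis by listings, so no revision interval will be computed. That lowers the urgency; it does not make the rule sound for the 140 randomized subjects for whom it was written.

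**What to change.** Reconcile Protocol 7.8.2, 9.1.9, 10.5 and 12.5/12.5.1 as follows:

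- State that, once operated, subjects remain on the existing visit schedule to 12 months for data collection unless consent is withdrawn or there is death, loss to follow-up, or study or site termination.
- In 7.8.2, limit the adverse event, concurrent illness, noncompliance and catch-all grounds to the period before surgery, together with the lead-in wording that leaves the list open. Deleting the named grounds alone would not be enough, because the open wording would still admit them.
- Align 9.1.9 and 12.5/12.5.1, so that follow-up of an ongoing event adds to the scheduled visits and does not replace them.
- In 10.5, redefine the category for adverse events leading to study discontinuation to match, and say how incomplete follow-up is counted in the revision proportion.
- Reconcile the medication wording in 7.8.2 and 9.1.9 with 9.1.8. While 9.1.8 stands as it is, the wording has no object and should come out. Whether anything ought to be restricted is a clinical question outside this point.

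This concerns data collection only; it changes nothing in clinical care, and the right to withdraw consent in 7.8.3 is untouched. The cost is continued visit effort for these subjects, on visits already scheduled, and aligning several sections. For the study as it ended, SAP 7.6 marks disposition as not applicable, so the final report should state whether any of the four subjects left because of an adverse event and how far each was followed.
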